## 1.0 OBJECTIVES / SPECIFIC AIMS

The objective of this study is to establish the safety, feasibility, tolerability, and acceptability of high-dose accelerated intermittent theta burst (iTBS) repetitive transcranial magnetic stimulation (rTMS) to the left dorsolateral prefrontal cortex (dlPFC) in patients with amnestic Mild Cognitive Impairment (aMCI). We also seek to obtain preliminary efficacy data as well as feasibility / acceptability data of computerized cognitive training as an adjunct to iTBS rTMS. The long-term goal of this project is to obtain preliminary data to support future empirical studies of iTBS rTMS for aMCI, including future randomized controlled trials to devise the optimum rTMS therapeutic delivery (with variations in dosing parameters, cortical targeting, and MCI syndrome indications), with the ultimate goal of dementia prevention. *The scientific merit of this pilot study has been peer-reviewed and subsequently recommended for funding through the National Center of Neuromodulation for Rehabilitation (NC NM4R).*

**AIM 1: Establish the safety of an accelerated rTMS protocol for neurocognitive rehabilitation in aMCI.** We hypothesize that accelerated rTMS will be safe as indexed by 1) no clinically significant structural brain changes; 2) no decrements in neurocognitive function; 3) no significant adverse events.

**AIM 2: Establish the feasibility, tolerability, and acceptability of an accelerated rTMS protocol for neurocognitive rehabilitation in aMCI.** We hypothesize that 1) aMCI patients will consider the treatment acceptable and that 2) recruitment and retention will be feasible (> 80% retention).

**EXPLORATORY AIM: Establish the preliminary efficacy of an accelerated rTMS protocol for neurocognitive rehabilitation in aMCI.** We hypothesize that aMCI patients will demonstrate modest improvements on neurocognitive testing and self-reported affective symptoms and quality of life from pre- to post-treatment.

**EXPLORATORY AIM: Establish the feasibility, acceptability of computerized cognitive training as an adjunct to accelerated rTMS in MCI.** We hypothesize that aMCI patients will complete a range of exercises between sessions and at home (feasibility) and will rate the intervention as productive (acceptability).

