In this open-label, safety and feasibility trial, we will recruit 40 amnestic MCI (aMCI) patients (target completers N=30) through memory disorders and neuropsychology clinics, as overseen by PI and neuropsychologist [name]. We will recruit clinically well-defined participants who will meet stringent actuarial neuropsychological criteria for aMCI. **This study will employ identical procedures to an ongoing IRB-I approved NC NM4R pilot, *Neuromodulation and Plasticity in Cognitive Control Neurocircuitry in Chronic Stroke* (PI: [name]; Pro 83136).** Specifically, neuronavigation-based targeting of the left dorsolateral prefrontal node of the cognitive control network will be performed. This study will utilize accelerated rTMS using a MagVenture MagPro TMS System. All participants will receive treatment for eight, 3-min sessions of iTBS on each of three days within an eight-day span. Each session would be separated by 10 mins or more per participant comfort and convenience. To collect preliminary feasibility and acceptability data for a planned follow-up combinatorial intervention study, participants will complete computerized cognitive exercises in the intervening periods between same-day rTMS sessions. At pre- and post-treatment, participants will undergo brain MRI (FLAIR, diffusion, T2\*/gradient, volumetric scans, resting state) and computerized neurocognitive testing. As an open-label pilot study, there is no sham control group.

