## 6.0 NUMBER OF SUBJECTS

The target completion is 30 participants. To contend with attrition, we propose to enroll 40 participants.

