## 11.0 SPECIMEN COLLECTION AND BANKING (Not Applicable)

## 12.0 DATA MANAGEMENT

### *Analysis*

Aim 1. FLAIR, diffusion, T2\*/gradient, perfusion and volumetric scans will be reviewed by [name] for any new signal abnormality. Adverse events will be surveyed and summarized.

Aim 2. Retention (i.e., defined as completion of all study sessions) will be determined. Participants will also complete a survey regarding acceptability, including qualitative responses for treatment modification.

Exploratory Aim 3. Neurocognitive performance and affective symptoms/quality of life will be analyzed with repeated-measures mixed models.

Exploratory Aim 4. BrainHQ usage/retention, performance, and acceptability will be analyzed with repeated-measures mixed models.

**Power Considerations.** The aims of this study are to determine safety and feasibility. The retention rate of 80% was determined to ensure that recruitment in the planned follow-up studies would be feasible in the longer time span allowed by future grants. Although these results will not be as compelling in the absence of a sham control, these data will give us an estimate of the

potential effect sizes and response variability that we can anticipate in future randomized controlled trials.

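### Aim 1 would read safety from an absence of significant adverse events, but zero events in 30 to 40 patients leaves per-patient rates up to about 9–12% open, and *significant* is undefined

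*Combined protocol and SAP*

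**What the plan says.** Section 1.0 (Objectives / Specific Aims) frames Aim 1 as establishing the safety of the accelerated schedule in aMCI. The hypothesis rests on three indices: structural brain change, neurocognitive decline and "3) no significant adverse events". Section 4.0 (Study Endpoints) lists adverse events among the Aim 1 primary outcomes.

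In section 12.0, the whole planned analysis of this index is "Adverse events will be surveyed and summarized". Power Considerations says "The aims of this study are to determine safety and feasibility", but the only figure it discusses is the 80% retention rate.

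Section 6.0 explains the sample size by attrition alone: "The target completion is 30 participants. To contend with attrition, we propose to enroll 40 participants". Section 2.0 adds that "As an open-label pilot study, there is no sham control group".

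Section 13.0 defines an adverse event (any undesired change during the trial, with no causal condition) and a serious adverse event (which includes inpatient hospitalization, again with no causal condition). It does not define a significant adverse event. It does have staff assess severity, seriousness, relatedness and expectedness for each event, and it sends severe scores on the side-effect form to the PI within 24 hours.

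**The concern.** The aim is worded as a conclusion (safety established), and one of its indices is an absence of events. Nothing in the plan attaches uncertainty to that absence. A reader of the results would see no events and a statement of safety, with no indication of what rate the data leave open.

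This matters here for three reasons. Section 2.0 says the safety of this schedule has not yet been shown in MCI. Section 15.0 names seizure as the main safety concern and describes the earlier accelerated-rTMS evidence as coming from people without neurological disease. The results are also meant to support later randomized trials. Without a control arm there is no comparison rate to put a count in context, so an interval is the least that is needed to read it.

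The undefined term is a second weakness. In an open-label study, whether a given event counts as significant could be settled after the event is known.

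**Working it through.** **The plan's own figure.** Enrolment of 40 for 30 completers follows from 30 / (1 − 0.25) = 40, so the implied attrition is 25%. Using the 20% attrition that matches the retention target gives 30 / 0.80 = 37.5, or 38, which is close. The sample size is therefore an attrition calculation. The documents state no precision figure for adverse events, so there is none to reproduce.

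**Inputs.** n = 40 enrolled and n = 30 target completers (section 6.0); one arm (section 2.0). The plan states no confidence level, so I assume 95% and show both conventions. The number treated is not stated. If enrolment and the completer target are both met, it lies between 30 and 40.

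**What zero events excludes.** The exact (Clopper-Pearson) upper limit for 0/n is 1 − a^(1/n), with a = 0.025 two-sided and a = 0.05 one-sided.

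| n | Two-sided 95% upper limit | One-sided 95% upper limit |
|---|---|---|
| 40 | 1 − 0.025^(1/40) = 8.8% | 1 − 0.05^(1/40) = 7.2% |
| 30 | 1 − 0.025^(1/30) = 11.6% | 1 − 0.05^(1/30) = 9.5% |

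**How often zero would be seen.** P(0 events) = (1 − p)^n. The true rates p are illustrative, since the documents give none.

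| True per-patient rate | n = 40 | n = 30 |
|---|---|---|
| 1% | 0.67 | 0.74 |
| 2% | 0.45 | 0.55 |
| 5% | 0.13 | 0.21 |

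A clean result is thus about an even chance at a 2% rate and uncommon at 5%.

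**If one event occurs.** The exact two-sided 95% interval is 0.06% to 13.2% for 1/40 and 0.08% to 17.2% for 1/30. The upper limit moves by about 4 to 6 percentage points from the zero-event case, while a hypothesis of no events goes from met to not met.

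**Scale.** To exclude 2% with zero events (two-sided) takes ln(0.025) / ln(0.98) = 182.6, so 183 patients. To exclude 5% takes ln(0.025) / ln(0.95) = 71.9, so 72. These show what the design cannot do. They are not a proposal to enlarge it.

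**Which events count.** Three readings of *significant* fit the text: serious as defined in section 13.0, clinically significant, or treatment-related. Under the first, with cause ignored, an unrelated hospitalization counts against the hypothesis. Under the third it does not. Relatedness is recorded per event and enters the IRB reporting criteria in section 13.0, but nothing links it to Aim 1.

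**The case against.** The best defence is that this is a pilot. Adverse events are one of three indices, the analysis is descriptive, and the plan sets no pass/fail test. The data needed for a proper summary are already collected, a DSMB with a biostatistician oversees the trial, and exact intervals could be added at reporting. All of that stands. It means that nothing is lost in data collection and that no formal test or larger sample is called for. It does not answer the mismatch between an aim of establishing safety and a summary with no stated uncertainty.

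Three stronger readings are tempting, and the documents do not support them.

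- *That one unrelated hospitalization would fail the hypothesis.* This needs *significant* to mean serious and cause to be irrelevant. The text permits that but does not state it. Some of it leans the other way: IRB reporting of events other than deaths requires possible relatedness, and the DSMB's power to halt the trial concerns harm caused by the intervention. How often such a hospitalization would occur needs a background rate that the documents do not give.
- *That zero events is likely even if serious events are fairly common.* At a 5% rate the probability of zero is only 0.13 to 0.21.
- *That the plan contains a formal all-zero decision rule.* It contains a hypothesis and a descriptive summary.

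**Conclusion.** The concern holds in a limited form. Zero events in this single-arm study would be compatible, at two-sided 95% confidence, with per-patient rates up to 8.8% if 40 are treated and 11.6% if 30 are, so it cannot by itself establish safety. *Significant* is undefined and has no attribution rule, so the hypothesis cannot be judged unambiguously in either direction.

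The limits assume that each patient is counted once, that patients are independent, and that between 30 and 40 receive treatment. The 95% level is my assumption, as the plan states none. I rate this a should-fix: it changes what the trial may conclude, but it does not change whom it enrols or what it collects.

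**What to change.** In section 1.0 (Aim 1) and section 12.0 (Analysis, Aim 1, and Power Considerations):

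1. Define the events that count, using categories the protocol already captures: seizure, treatment-related serious adverse events, and treatment-related ratings of severe on the side-effect form.
2. For each, report the number of patients with the event over all patients who received at least one iTBS session, with an exact two-sided 95% interval. Neither completers nor all enrolled is the right denominator. Completers omit patients who stop because of an event, and some enrolled patients may leave before any stimulation (section 14.0 allows withdrawal for not tolerating the first MRI).
3. List unrelated events separately.
4. State in Power Considerations the two-sided upper limit for zero events at the number treated: 8.8% if 40, 11.6% if 30. Use the same convention there as in the reported interval.
5. Word the conclusion as the rate excluded, not as safety established.

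Settle the definitions before outcomes are reviewed. The cost is a few sentences and a few lines of analysis, with no added patients or procedures. The downside is a less favourable headline.

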## 2.0 BACKGROUND

Mild Cognitive Impairment (MCI) is the pre-dementia stage in which individuals remain functionally intact yet demonstrate the early cognitive and behavioral changes of neurodegenerative diseases. Over half of those with MCI develop dementia within 10 years, but an intervention that can delay dementia onset by 5 years may cut dementia prevalence by a third and decrease healthcare costs. However, the diagnosis and treatment of MCI is hampered by its variability in underlying etiology and clinical presentation. That is, the neuropathology of MCI is markedly heterogeneous, and neuropsychiatric symptoms are also highly comorbid, including depression, anxiety, apathy, and sleep dysfunction. Thus, *the ideal MCI intervention must suit a pathologically and behaviorally heterogeneous condition and have a high potential to be disseminated for dementia prevention.*

Repetitive transcranial magnetic stimulation (rTMS) to left dorsolateral prefrontal cortex (dlPFC) is one such potential intervention. One hypothesized mechanism of action of this approach is the enhancement of cognitive control by targeting the neurocircuit substrates, leading to improved

affect regulation. If so, then rTMS should be a powerful transdiagnostic intervention for both affective and cognitive symptoms. Indeed, rTMS has been shown to reduce these symptoms in various neuropsychiatric syndromes including geriatric depression, with the specific literature on rTMS for MCI currently nascent yet promising.

Conventionally, a course of rTMS is 30-40 minutes of treatment each weekday for 4-6 weeks. To lessen burden while leveraging established outcomes, newer *high-dose accelerated intermittent theta burst (iTBS) rTMS* protocols increase the number of sessions per day, reducing the treatment course by >50% and yielding more rapid response and remission while retaining safety, feasibility, acceptability, and effectiveness. However, the safety and feasibility of this delivery schedule has yet to be established for MCI.

In this open-label, safety and feasibility trial, we will recruit 40 amnestic MCI (aMCI) patients (target completers N=30) through memory disorders and neuropsychology clinics, as overseen by PI and neuropsychologist [name]. We will recruit clinically well-defined participants who will meet stringent actuarial neuropsychological criteria for aMCI. **This study will employ identical procedures to an ongoing IRB-I approved NC NM4R pilot, *Neuromodulation and Plasticity in Cognitive Control Neurocircuitry in Chronic Stroke* (PI: [name]; Pro 83136).** Specifically, neuronavigation-based targeting of the left dorsolateral prefrontal node of the cognitive control network will be performed. This study will utilize accelerated rTMS using a MagVenture MagPro TMS System. All participants will receive treatment for eight, 3-min sessions of iTBS on each of three days within an eight-day span. Each session would be separated by 10 mins or more per participant comfort and convenience. To collect preliminary feasibility and acceptability data for a planned follow-up combinatorial intervention study, participants will complete computerized cognitive exercises in the intervening periods between same-day rTMS sessions. At pre- and post-treatment, participants will undergo brain MRI (FLAIR, diffusion, T2\*/gradient, volumetric scans, resting state) and computerized neurocognitive testing. As an open-label pilot study, there is no sham control group.

### 3.0 INTERVENTIONS TO BE STUDIED

**Accelerated rTMS.** We will utilize an LTP-like accelerated iTBS rTMS targeted to left dlPFC in aMCI using a MagVenture MagPro TMS System. All participants will receive treatment for eight, 3-minute sessions on each of three days within an eight-day span. Each session will be separated by 10 minutes, according to participant comfort and preference. As an open-label pilot investigation, there is no sham control group.

**RATIONALE:** Transcranial magnetic stimulation (TMS) is a means of non-invasively activating neuronal elements in the brain. Repetitive TMS (rTMS) in particular causally influences neural networks and produces acute neuroplastic periods that reliably persist after the termination of stimulation and promote cortical remodeling. The evidence base for therapeutic rTMS has been most persuasive in the case of depression treatment. Proposed as a means of up-regulating prefrontal control over dysregulated limbic activation, high-frequency rTMS is most often applied to left dorsolateral prefrontal cortex (dlPFC). Several meta-analyses have now shown that open-label effects sizes are large, while comparisons to sham stimulation are at least moderate to large among even patients highly resistant to pharmacotherapy. In geriatric depression, the FDA-

approved course of rTMS has been found to be safe, tolerable, and yield commensurate response rates.

*The proposed mechanism by which rTMS remediates depression implies that rTMS should also be a powerful transdiagnostic intervention for both cognitive and affective dysregulation.* The left dlPFC site typically targeted with rTMS is seated in an area of cortex integral to intact higher order cognition (i.e., executive function). Co-I [name] has shown in a large meta-analytic study that this left dlPFC region (as well as the rest of the cognitive control or multiple demand network) is commonly hypo-activated during cognitive tasks across neuropsychiatric disorders. While dementia was not included in this meta-analysis, a similar meta-analysis of task-based fMRI identifies prominent hypoactivation in MCI in the same frontoparietal network. Thus, it is unsurprising that other meta-analyses and reviews of mild to moderate AD have shown that rTMS improves cognitive ability and neuropsychiatric symptoms with no adverse cognitive effects. Although research into using rTMS as a treatment for MCI is in its infancy, it is an ideal disease stage for dementia prevention using rTMS particularly given that 25-40% of MCI patients have comorbid depression which in turn increases risk of further cognitive decline and dementia. Thus, *there is abundant preliminary data supporting our rationale to use rTMS of the dlPFC to target neurocircuitry integral to cognitive and affective dysfunction, although its delivery could be better optimized to support clinical application.*

A therapeutic course of rTMS typically consists of 30-40 minutes of high-frequency (i.e. 10 Hz) treatment on each weekday, for 4-6 weeks. This schedule can be burdensome and reduce adherence. To improve upon this conventional approach, Co-I [name] et al. pioneered accelerated rTMS, demonstrating that delivering 3 high-dose sessions per day (i.e. 10 Hz; 3,000 pulses for 30 mins; 18,000 pulses/day total) on three consecutive days was safe, feasible, and suggestive of rapid antidepressant effects. More recently, a number of groups have demonstrated the feasibility, acceptability, and effectiveness of this form of delivery in which sessions are repeated daily, typically spaced by at least 30 minutes, to reduce total days of treatment. Safety has also been assessed with both structural and metabolic imaging as well as neurocognitive testing, which has shown no adverse effects and modest gains in cognition. Furthermore, acceptability studies show that accelerated rTMS increases adherence and decreases interruptions to daily obligations while yielding faster response. Importantly, critical to the success of this project is the fact that the procedures proposed in this study have already been approved by the MUSC Institutional Review Board for an NM4R pilot grant (PI: [name]: Pro 83136). As such, all methods are already established and running, personnel trained, and, importantly, we will be able to compare the results in two prevalent and functionally impairing neurodegenerative disorders.

**Computerized Cognitive Training.** To collect preliminary feasibility/acceptability data for a planned follow-up combinatorial intervention study, participants will complete computerized cognitive exercises in the intervening periods between same-day rTMS sessions. Clinical trials using the online system Brain HQ (<https://www.brainhq.com/world-class-science/science-team>) have been shown to be associated with cognitive function in older adults. Each exercise takes approximately 3-10 minutes and adapts to the individual's progress. The exercises fall under one of six categories: processing speed, memory, attention, people skills, cognitive flexibility and spatial navigation. During breaks between treatments, participants will complete exercises for a total of 20 minutes of exercises per day and 60 minutes of exercises over the

three days of treatment. Afterwards, participants will be asked to complete at least 20 minutes of these exercises per day at home during the 4 weeks following treatment completion.

**RATIONALE:** Because accumulating work suggests that the 10-60 minute window following excitatory rTMS is a window of particular neuroplasticity, the longer-term plan of this line of work is to utilize rTMS as an adjunct for multimodal interventions including computerized cognitive training and behavioral interventions to optimize neuroplasticity, cognitive remediation, and quality of life. Toward this goal, we will collect preliminary acceptability/feasibility data of computerized cognitive exercises, interleaved between rTMS sessions.

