**Sessions 3-5: rTMS (2 – 3 hours).** A MagVenture MagPro TMS System will be utilized. All participants will receive open-label treatment for approximately eight, 3-minute sessions of intermittent theta burst rTMS on each of three days within an eight-day span. A single session=600 pulses at 120% rMT, iTBS triplets at 50 Hz for 2 s and repeated every 10 s for a total of 190 s to left dlPFC. Total pulses=14,400. To enable adherence and retention, the days do not need to be contiguous. Same day sessions will be separated by 10-15 minutes, but more accounting for participant comfort. After each day of treatment, participants will be asked to complete an rTMS acceptability questionnaire. During treatment breaks participants will complete Momentary Assessment of TMS and 10-15 minutes of Brain HQ exercises between each session and will also have the option of completing tasks at home on intervening days during the treatment schedule. At the end of the final treatment session, participants will be asked to rate the exercises based on difficulty and enjoyment.

**Session 6: In-person Post-treatment Neurocognitive/Neuropsychiatric Assessment (2 - 3 hours).** Within one week following treatment, participants will repeat the pre-treatment neuropsychiatric and neurocognitive assessment for assessment of pre/post treatment changes.

**Session 7: Post-treatment MRI Scans (1 - 2 hours).** Within one week following treatment, participants will repeat the pre-treatment MRI scans for assessment of pre/post treatment changes.

**Session 8: 1 – 3 weeks post-treatment completion.** During the intervening weeks after Sessions 6/7 and before Session 9, the participants will be asked to remotely complete surveys using REDCap. Participants will also be provided with a research account for BrainHQ and asked to engage in at least 20 minutes of brain exercises daily until Session 9.

**Session 9: 4 weeks post-treatment completion.** Participants will again be asked to complete surveys using REDCap. Participants will also be asked to complete the MoCA remotely, as well as acceptability/satisfaction questionnaires regarding the rTMS and BrainHQ interventions.

**Participant Compensation.** Participants will be compensated as follows:

Consent & Session 1:	\$40 for screening and pre-treatment assessments
Session 2:	\$50 for the pre-treatment MRI
Sessions 3 to 5:	\$120 for rTMS treatment (i.e. \$40/day)
Sessions 6 and 7:	\$100 for post-treatment assessments and MRI

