Potential worsening of neuropsychiatric symptoms with TMS. Several studies have thus far demonstrated the feasibility of using rTMS in depression without any alarming indicators of exacerbation of symptoms. The research team will work closely with patients to familiarize them with the nature of this experimental setup. All staff will also be trained to be alert to any worsening of neuropsychiatric symptoms and/or psychosocial impairment. Bipolar patients have at times shown hypomanic or manic switches in the course of once-daily rTMS, as such patients with bipolar type I will be excluded. Additionally, all patients will be assessed throughout each day for worsening symptoms. Participants will similarly be queried for worsening suicidal ideation/intent. Drs. [name] or [name] will additionally assess each patient once per week in-person or via telephone during rTMS treatment and the one month study involvement to assess mood, functioning, and safety.

Potential risk of a seizure with TMS. There is a risk that TMS can cause a seizure; but it is rare. The risk of seizure induction is related to the intensity, duration, frequency and rest interval of stimulation. Following the adoption and widespread use of the safety guidelines from a National Institute of Neurological Disorders and Stroke (NINDS) workshop on TMS, only 20 seizures have been reported since 1997, and they usually involved parameters of "higher settings" than the "safe range". To our knowledge, stimulation with the parameters and settings proposed in this study should not cause seizures. Each subject's stimulus intensity is determined by his or her motor threshold and will be carefully calculated before beginning treatment. In this study participants will receive rTMS to the prefrontal cortex, a region far less prone to seizure. Nonetheless, we will watch participants closely for any signs of seizure throughout all procedures. Additionally, our study patients will be free from using known stimulants and medications that are known to increase the risk of seizure (e.g., theophylline).

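### The gap between same-day iTBS sessions is worded three ways, and the tasks assigned to it do not fit its nominal 10 minutes and contradict the stated daily BrainHQ total

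*Combined protocol and SAP*

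**What the plan says.** Three places set the gap between same-day sessions:

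- Section 2.0 (Background), final paragraph: "Each session would be separated by 10 mins or more per participant comfort and convenience".
- Section 3.0 (Interventions), Accelerated rTMS: "Each session will be separated by 10 minutes, according to participant comfort and preference".
- Section 10.0 (Study Design and Methods), Sessions 3-5: "Same day sessions will be separated by 10-15 minutes, but more accounting for participant comfort".

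Two places say what happens in the gaps:

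- Section 10.0, Sessions 3-5: "During treatment breaks participants will complete Momentary Assessment of TMS and 10-15 minutes of Brain HQ exercises between each session".
- Section 3.0, Computerized Cognitive Training: "participants will complete exercises for a total of 20 minutes of exercises per day and 60 minutes of exercises over the" three treatment days. The same paragraph says "Each exercise takes approximately 3-10 minutes".

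Two further statements bear on the gap. The rationale in Section 3.0 describes other accelerated schedules as ones in which "sessions are repeated daily, typically spaced by at least 30 minutes, to reduce total days of treatment". Section 15.0, under the risk of seizure, says "The risk of seizure induction is related to the intensity, duration, frequency and rest interval of stimulation". The procedures table in Section 10.0 allots 2 to 3 hours to each treatment day.

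**The concern.** The gap is part of the schedule whose safety Aim 1 is meant to establish. Sections 2.0 and 10.0 both start at 10 minutes and allow lengthening only. Section 3.0 lets comfort and preference act on the 10 minutes with no direction and no explicit floor. A delivery parameter should not have to be inferred from other sections.

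The break contents make this a practical problem. Staff who follow Section 10.0 on BrainHQ cannot also keep to a 10-minute gap, and they will far exceed the daily total in Section 3.0. Two things are at stake. The Aim 1 safety summary would describe a schedule whose spacing was neither fixed nor recorded. And rate of BrainHQ usage, the primary outcome of the second exploratory aim in Section 4.0, would have no single prescribed amount to be judged against.

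**Working it through.** **Inputs.** Eight sessions per day on three days (Section 3.0), so 8 − 1 = 7 gaps per day. Each session is 600 pulses over 190 s (Section 10.0). BrainHQ is 10–15 min per gap (Section 10.0) or 20 min per day (Section 3.0). The visit lasts 2–3 hours (Section 10.0 table). The length of the Momentary Assessment is not stated; I assume 1–5 min.

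**1. The plan's own dose figure.** 600 × 8 × 3 = 14,400 pulses, as Section 10.0 states. The session count is therefore sound, and the problem lies only in the gaps.

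**2. Does the Section 10.0 load fit the gap?** Load per gap = BrainHQ + assessment.

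- Assessment 1 min: 10 + 1 = 11 to 15 + 1 = 16 min.
- Assessment 5 min: 10 + 5 = 15 to 15 + 5 = 20 min.

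A 10-minute gap falls short by 1–6 min in the first case and 5–10 min in the second. At the lowest BrainHQ load it falls short by whatever the assessment takes. This applies to the 10 minutes in Section 3.0 and equally to the lower end in Sections 2.0 and 10.0.

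**3. The two BrainHQ loads.**

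| | Per day | Three days | Mean per gap |
|---|---|---|---|
| Section 10.0 | 7 × 10 to 7 × 15 = 70–105 min | 210–315 min | 10–15 min |
| Section 3.0 | 20 min | 60 min | 20 / 7 = 2.9 min |

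The ratio is 70 / 20 = 3.5 to 105 / 20 = 5.25. A participant who does exactly 20 min a day has met Section 3.0 in full, but only 20 / 105 = 19% to 20 / 70 = 29% of Section 10.0. The lighter load leaves 10 − 2.9 = 7.1 min per 10-minute gap on average, enough for an assessment of the assumed length.

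**4. What the visit length allows.** Stimulation takes 8 × 190 / 60 = 25.3 min. Day length = 25.3 + 7 × gap.

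- Gap 10 min: 95.3 min.
- Gap 15 min: 130.3 min.
- Gap 30 min: 235.3 min.

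Turned round, mean gap = (visit − 25.3) / 7:

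- 2 hours: (120 − 25.3) / 7 = 13.5 min.
- 3 hours: (180 − 25.3) / 7 = 22.1 min.

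These are upper limits, because set-up is ignored. They are compatible with Sections 2.0 and 10.0 and longer than the 10 minutes in Section 3.0. A 10-minute gap would fill the shorter visit only if set-up took 120 − 95.3 = 24.7 min, so visit length does not settle which rule is meant.

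**5. Comparison with the spacing described for other schedules.** The nominal 10–15 min is 10 / 30 = 33% to 15 / 30 = 50% of the 30-minute figure. The mean gap the visit allows is up to 13.5 / 30 = 45% to 22.1 / 30 = 74% of it. The documents do not discuss the difference. The table of accelerated studies in Section 15.0 has no column for spacing between sessions; its interval entries stand beside train lengths under the frequency heading.

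**The case against.** The strongest reply is that this is loose drafting around one intention. All three wordings contain 10 minutes. Section 10.0 is the operative procedure, and it and Section 2.0 both point upward only. A reader might infer that Section 3.0 permits staff to shorten a break at a participant's request. It does not say so, and the two parallel sentences suggest otherwise. That part of the reply stands: what is missing in Section 3.0 is an explicit floor, and no permission to go below 10 minutes is given.

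A reader might also infer that a short gap is shown to raise seizure risk. The documents do not support that. Section 15.0 lists rest interval among the related factors without saying whether it means the pause between trains or between sessions, and it gives no figure linking gap length to risk. Nor does Section 3.0 attach the 30-minute spacing to safety evidence: that sentence speaks of feasibility, acceptability and effectiveness, and safety comes in the next sentence, with no spacing given. The word typically, and the varied protocols tabulated in Section 15.0, also prevent a like-for-like benchmark.

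Finally, the time shortfall disappears under the Section 3.0 BrainHQ load, and Section 10.0 allows longer gaps. Both points are right. They move the problem without removing it, since the two BrainHQ loads still cannot both be followed. Prior ethics approval of the same procedures in a related pilot, cited in Sections 2.0 and 3.0, is relevant context, but it does not show which wording applies here. With a single arm there is no between-group comparison to bias; what suffers is the description of what was delivered.

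**Conclusion.** The inconsistency is real and should be corrected. It is not a demonstrated safety defect. The interval rule differs across three sections that share a nominal 10 minutes, and the section defining the intervention gives no explicit floor. The larger numerical conflict is in the break contents: 70–105 against 20 minutes of BrainHQ per day, a factor of 3.5 to 5.25. The heavier load does not fit a 10-minute gap for any assessment time above zero.

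The BrainHQ totals rest on reading Section 10.0 as placing exercises in all 7 gaps, which is what it says. The size of the shortfall per gap, 1 to 10 minutes, rests on the assumed 1–5 minute assessment. The mean gap of 13.5–22.1 minutes ignores set-up. No conclusion is drawn about the effect of gap length on risk.

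**What to change.** - The clinical investigators should reconcile Sections 2.0, 3.0 and 10.0 into one interval rule, stating whether it is a floor, a fixed value or a range. No interval is proposed here.
- They should reconcile the BrainHQ load in Sections 3.0 and 10.0, so that there is one prescribed amount, it fits the chosen interval together with the assessment, and usage can be reported against it.
- They should comment on how the chosen interval relates to the 30-minute spacing in the Section 3.0 rationale, and say in Section 15.0 which rest interval is meant.
- Staff should record the start time of every iTBS session. The Aim 1 analysis in Section 12.0 should report the distribution of achieved gaps alongside the adverse-event summary.

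The cost is a short protocol amendment and one time field per session on the treatment form. With 24 sessions per participant (8 × 3), that is 24 time entries each.
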